N18.3	ICD10	Chronic kidney disease, Stage 3 (moderate)				
N18.4	ICD10	Chronic kidney disease, Stage 4 (severe)				
N18.9	ICD10	Chronic kidney disease, unspecified				
Z94.0	ICD10	Kidney transplant status				
403.00	ICD9	Hypertensive chronic kidney disease, malignant, with chronic kidney disease stage I through stage IV, or unspecified				
403.10	ICD9	Hypertensive chronic kidney disease, malignant, with chronic kidney disease stage I through stage IV, or unspecified				
403.90	ICD9	Hypertensive chronic kidney disease, unspecified, with chronic kidney disease stage I through stage IV, or unspecified				
404.00	ICD9	Hypertensive heart and chronic kidney disease, malignant, without heart failure and with chronic kidney disease stage I through stage IV, or unspecified				
404.01	ICD9	Hypertensive heart and chronic kidney disease, malignant, with heart failure and with chronic kidney disease stage I through stage IV, or unspecified				
404.10	ICD9	Hypertensive heart and chronic kidney disease, benign, without heart failure and with chronic kidney disease stage I through stage IV, or unspecified				
404.11	ICD9	Hypertensive heart and chronic kidney disease, benign, with heart failure and with chronic kidney disease stage I through stage IV, or unspecified				
404.90	ICD9	Hypertensive heart and chronic kidney disease, unspecified, without heart failure and with chronic kidney disease stage I through stage IV, or unspecified				
404.91	ICD9	Hypertensive heart and chronic kidney disease, unspecified, with heart failure and with chronic kidney disease stage I through stage IV, or unspecified				
582	ICD9	Chronic glomerulonephritis				
583	ICD9	Nephritis/nephropathy				
585.1	ICD9	Chronic kidney disease, Stage I				
585.2	ICD9	Chronic kidney disease, Stage II (mild)				
585.3	ICD9	Chronic kidney disease, Stage III (moderate)				
585.4	ICD9	Chronic kidney disease, Stage IV (severe)				
585.9	ICD9	Chronic kidney disease, unspecified				

CODE	TYPE	DESCRIPTION					
V42.0	ICD9	Kidney replaced by transplant					
E08	ICD10	Diabetes mellitus due to underlying condition					
E09	ICD10	Drug or chemical induced diabetes mellitus					
E10	ICD10	Type 1 diabetes mellitus					
E11	ICD10	Type 2 diabetes mellitus					
E13	ICD10	Other specified diabetes mellitus					
250.4	ICD9	Diabetes with renal manifestations					
250.5	ICD9	Diabetes with ophthalmic complications					
250.6	ICD9	betes with neurological manifestations					
250.7	ICD9	Diabetes with peripheral circulatory disorders					
G04.1	ICD10	Tropical spastic paraplegia					
G11.4	ICD10	Hereditary spastic paraplegia					
G80.0	ICD10	Spastic quadriplegic cerebral palsy					
G80.1	ICD10	Spastic diplegia cerebral palsy					
G80.2	ICD10	Spastic hemiplegic cerebral palsy					
G81	ICD10	Hemiplegia and hemiparesis					
G82	ICD10	araplegia (paraparesis s) and quadriplegia					
G83	ICD10	ther paralytic syndromes					
334.1	ICD9	ereditary spastic paraplegia					
342	ICD9	emiplegia and hemiparesis					
343	ICD9	Infantile cerebral palsy					
344	ICD9	Other paralytic syndromes					
I85.0	ICD10	Esophageal varices					
I86.4	ICD10	Gastric varices					
K70.4	ICD10	Alcoholic hepatic failure					
K71.1	ICD10	Toxic liver disease with hepatic necrosis					
K72.1	ICD10	Chronic hepatic failure					
K72.9	ICD10	Hepatic failure, unspecified					
K76.5	ICD10	Hepatic veno-occlusive disease					
K76.6	ICD10	Portal hypertension					
K76.7	ICD10	Hepatorenal syndrome					
456.0	ICD9	Esophageal varices with bleeding					
456.1	ICD9	Esophageal varices without mention of bleeding					
456.2	ICD9	Esophageal varices in diseases classified elsewhere					
572.2	ICD9	Hepatic encephalopathy					
572.3	ICD9	Portal hypertension					
572.4	ICD9	Hepatorenal syndrome					
572.8	ICD9	Other sequelae of chronic liver disease					
I12.0	ICD10	Hypertensive chronic kidney disease with stage 5 chronic kidney disease or end stage renal disease					

CODE	TYPE	DESCRIPTION				
I13.11	ICD10	Hypertensive heart and CKD without heart failure with stage 5 chronic kidney disease, or end stage renal disease				
I13.2	ICD10	Hypertensive heart and chronic kidney disease with heart failure and with stage 5 chronic kidney disease, or end stage renal disease				
N18.5	ICD10	Chronic kidney disease, Stage 5				
N18.6	ICD10	End stage renal disease				
N19	ICD10	Unspecified kidney failure				
N25.0	ICD10	Renal osteodystrophy				
Z49	ICD10	Encounter for care involving renal dialysis				
Z99.2	ICD10	Dependence on renal dialysis				
403.01	ICD9	Hypertensive chronic kidney disease, malignant, with chronic kidney disease stage V or end stage renal disease				
403.11	ICD9	Hypertensive chronic kidney disease, benign, with chronic kidney disease stage V or end stage renal disease				
403.91	ICD9	Hypertensive chronic kidney disease, unspecified, with chronic kidney disease stage V or end stage renal disease				
404.02	ICD9	Hypertensive heart and chronic kidney disease, malignant, without heart failure and with chronic kidney disease stage V or end stage renal disease				
404.03	ICD9	Hypertensive heart and chronic kidney disease, malignant, with heart failure and with chronic kidney disease stage V or end stage renal disease				
404.12	ICD9	Hypertensive heart and chronic kidney disease, benign, without heart failure and wi chronic kidney disease stage V or end stage renal disease				
404.13	ICD9	Hypertensive heart and chronic kidney disease, benign, with heart failure and chro kidney disease stage V or end stage renal disease				
404.92	ICD9	Hypertensive heart and chronic kidney disease, unspecified, without heart failure and with chronic kidney disease stage V or end stage renal disease				
404.93	ICD9	Hypertensive heart and chronic kidney disease, unspecified, with heart failure and chronic kidney disease stage V or end stage renal disease				
585.5	ICD9	Chronic kidney disease, Stage V				
585.6	ICD9	End stage renal disease				
586	ICD9	Renal failure NOS				
588.0	ICD9	Renal osteodystrophy				
V45.11	ICD9	Renal dialysis status				
V45.12	ICD9	Noncompliance with renal dialysis				
V56.0	ICD9	Encounter for extracorporeal dialysis				
V56.1	ICD9	Fitting and adjustment of extracorporeal dialysis catheter				
V56.2	ICD9	Fitting and adjustment of peritoneal dialysis catheter				
V56.31	ICD9	Encounter for adequacy testing for hemodialysis				
V56.32	ICD9	Encounter for adequacy testing for peritoneal dialysis				
V56.8	ICD9	Encounter for other dialysis				

BIOPSY AND IMAGING PROCEDURE CODES FOR CIRRHOSIS

CODE	ТҮРЕ	DESCRIPTION					
47000	HCPCS/CPT-4	Biopsy of liver, needle					
47001	HCPCS/CPT-4	Biopsy of liver, needle					
47100	HCPCS/CPT-4	Excision procedures on the liver					
0FB00ZX	ICD10 pcs	Excision of Liver, Open Approach, Diagnostic					
0FB03ZX	ICD10 pcs	Excision of Liver, Percutaneous Approach, Diagnostic					
0FB04ZX	ICD10 pcs	Excision of Liver, Percutaneous Endoscopic Approach, Diagnostic					
0FB10ZX	ICD10 pcs	Excision of Right Lobe Liver, Open Approach, Diagnostic					
0FB13ZX	ICD10 pcs	Excision of Right Lobe Liver, Percutaneous Approach, Diagnostic					
0FB14ZX	ICD10 pcs	Excision of Right Lobe Liver, Percutaneous Endoscopic Approach, Diagnostic					
0FB20ZX	ICD10 pcs	Excision of Left Lobe Liver, Open Approach, Diagnostic					
0FB23ZX	ICD10 pcs	Excision of Left Lobe Liver, Percutaneous Approach, Diagnostic					
0FB24ZX	ICD10 pcs	Excision of Left Lobe Liver, Percutaneous Endoscopic Approach, Diagnostic					
5012	ICD9 pcs	Open liver biopsy					
5011	ICD9 pcs	Closed liver biopsy (Closed (percutaneous) [needle] biopsy of liver)					
5014	ICD9 pcs	Laparoscopic liver bx (Laparoscopic liver biopsy)					
91200	HCPCS/CPT-4	Nonimaging liver elastography					
76700	HCPCS/CPT-4	Complete ultrasound examination of the abdomen					
76705	HCPCS/CPT-4	Ultrasound, abdominal, real time with image documentation					
BF45ZZZ	ICD10 pcs	Ultrasonography of Liver					
BF46ZZZ	ICD10 pcs	Ultrasonography of Liver and Spleen					
8874	ICD9 pcs	Dx ultrasound-digestive (Diagnostic ultrasound of digestive system)					
74181	HCPCS/CPT-4	MRI scan of abdomen					
74182	HCPCS/CPT-4	MRI scan of abdomen with contrast					
74183	HCPCS/CPT-4	MRI scan of abdomen before and after contrast					
74185	HCPCS/CPT-4	MRI scan of blood vessels of abdomen					
BF35Y0Z	ICD10 pcs	Magnetic Resonance Imaging (MRI) of Liver using Other Contrast, Unenhanced and Enhanced					
BF35YZZ	ICD10 pcs	Magnetic Resonance Imaging (MRI) of Liver using Other Contrast					
BF35ZZZ	ICD10 pcs	Magnetic Resonance Imaging (MRI) of Liver					
74150	HCPCS/CPT-4	CT imaging of the abdomen and pelvis					
74160	HCPCS/CPT-4	CT imaging of the abdomen					
74170	HCPCS/CPT-4	CT imaging of the abdomen with and without IV contrast					
BF2500Z	ICD10 pcs	Computerized Tomography of Liver using High Osmolar Contrast, Unenhanced and Enhanced					
BF250ZZ	ICD10 pcs	Computerized Tomography of Liver using High Osmolar Contrast					
BF2510Z	ICD10 pcs	Computerized Tomography of Liver using Low Osmolar Contrast, Unenhanced and Enhanced					
BF251ZZ	ICD10 pcs	Computerized Tomography of Liver using Low Osmolar Contrast					
BF25Y0Z	ICD10 pcs	Computerized Tomography of Liver using Other Contrast, Unenhanced and Enhanced					

CODE	ТҮРЕ	DESCRIPTION				
BF25YZZ	ICD10 pcs	Computerized Tomography of Liver using Other Contrast				
BF25ZZZ	ICD10 pcs	Computerized Tomography of Liver				
BF2600Z	ICD10 pcs	Computerized Tomography of Liver and Spleen using High Osmolar Contrast, Unenhanced and Enhanced				
BF260ZZ	ICD10 pcs	Computerized Tomography of Liver and Spleen using High Osmolar Contrast				
BF2610Z	ICD10 pcs	Computerized Tomography of Liver and Spleen using Low Osmolar Contrast, Unenhanced and Enhanced				
BF261ZZ	ICD10 pcs	Computerized Tomography of Liver and Spleen using Low Osmolar Contrast				
BF26Y0Z	ICD10 pcs	Computerized Tomography of Liver and Spleen using Other Contrast, Unenhanced and Enhanced				
BF26YZZ	ICD10 pcs	Computerized Tomography of Liver and Spleen using Other Contrast				
BF26ZZZ	ICD10 pcs	Computerized Tomography of Liver and Spleen				
BF2C00Z	ICD10 pcs	Computerized Tomography of Hepatobiliary System, All using High Osmolar Contrast, Unenhanced and Enhanced				
BF2C0ZZ	ICD10 pcs	Computerized Tomography of Hepatobiliary System, All using High Osmolar Contrast				
BF2C10Z	ICD10 pcs	Computerized Tomography of Hepatobiliary System, All using Low Osmolar Contrast, Unenhanced and Enhanced				
BF2C1ZZ	ICD10 pcs	Computerized Tomography of Hepatobiliary System, All using Low Osmolar Contrast				
BF2CY0Z	ICD10 pcs	Computerized Tomography of Hepatobiliary System, All using Other Contrast, Unenhanced and Enhanced				
BF2CYZZ	ICD10 pcs	Computerized Tomography of Hepatobiliary System, All using Other Contrast				
BF2CZZZ	ICD10 pcs	Computerized Tomography of Hepatobiliary System, All				
BW2000Z	ICD10 pcs	Computerized Tomography of Abdomen using High Osmolar Contrast, Unenhanced and Enhanced				
BW200ZZ	ICD10 pcs	Computerized Tomography of Abdomen using High Osmolar Contrast				
BW2010Z	ICD10 pcs	Computerized Tomography of Abdomen using Low Osmolar Contrast, Unenhanced and Enhanced				
BW201ZZ	ICD10 pcs	Computerized Tomography of Abdomen using Low Osmolar Contrast				
BW20Y0Z	ICD10 pcs	Computerized Tomography of Abdomen using Other Contrast, Unenhanced and Enhanced				
BW20YZZ	ICD10 pcs	Computerized Tomography of Abdomen using Other Contrast				
BW20ZZZ	ICD10 pcs	Computerized Tomography of Abdomen				

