7. SELECTION OF PATIENTS

7.1. Study Population

All patients who meet diagnostic criteria in each database between 01 Jun 2015 and 31 Dec 2021 and who meet the eligibility criteria will be considered for these studies.

All diagnosis, treatment, laboratory, and procedure codes used to identify patients and define study variables are listed in Appendix A.

The treatment group will be patients with PBC with a history of inadequate response or intolerance to UDCA who initiated OCA in the study window. The control group will be PBC patients with a history of inadequate response or intolerance to UDCA who were eligible but were not treated with OCA (or off-label fibrates) in the study window. The decision to treat a patient with OCA or UDCA is at the discretion of the treating physician and has been made independent from inclusion in each of the databases.

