7.3. Exclusion Criteria

A patient who meets **any** of the following criteria for a given index date is not eligible for inclusion:

- History or presence of other concomitant liver diseases before the index date (inclusive), including:
 - Acute or chronic hepatitis C virus infection
 - Acute or chronic hepatitis B infection

- Primary sclerosing cholangitis
- Active alcoholic liver disease
- Hepatocellular carcinoma
- Hepatorenal syndrome
- Hepatopulmonary syndrome
- Portopulmonary syndrome
- NASH
- History of non-skin malignancy or melanoma before the index date (inclusive)
- History of HIV before the index date (inclusive)
- Medical conditions that may cause non-hepatic increases in ALP:
 - Paget's disease during the 12-month period before the index date (inclusive)
 - Fractures within 3 months before the index date (inclusive)
- Patients with laboratory values indicative of hepatic decompensation or significant hepatobiliary injury before the index date (inclusive):
 - TB >3 mg/dL
 - ALP >10x ULN
 - ALT and/or AST >10x ULN
- History of liver transplant before the index date (inclusive)
- Evidence of OCA, fenofibrate, or bezafibrate use before the index date (inclusive)
- History or presence of any of the following hepatic decompensating events before the index date (inclusive):
 - Variceal bleeding
 - Ascites
 - Hepatic hydrothorax
 - Spontaneous bacterial peritonitis
 - Hepatic encephalopathy

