12.1. Data Collection and Transfer

12.1.1. Komodo Health

Komodo Health merges administrative claims across >350 health plans including commercial (63%); Medicaid (23%); Medicare (10%); dual eligible (<1%); and other (2%). The dataset represents more than 325 million unique patients in the US between June 2015 and July 2021. The datasets include all inpatient, outpatient, and procedure claims, as well as service dates, associated ICD-9 and ICD-10 codes, and provider data.

Data from each payer are tokenized, deidentified, and encrypted by the individual payer (see Section 12.2.2). Some examples of file formats Komodo Health intakes from sources include TXT, CSV, and DAT file types. Komodo Health commonly receives data as (but not limited to) comma-delimited, pipe-delimited, and tab-delimited files. A transit token specific to the payer and Komodo Health is used, and once received the data are de-encrypted, including a final patient token. Thirty-six percent of plans transfer their data through a Komodo Health secure FTP site; 64% of plans provide a secure FTP site to Komodo Health to retrieve the data. Komodo Health receives and stores data in AWS S3 buckets.

Plans provide uncurated (raw) data. Data cleaning, such as deduplication, will be specified in the supplemental submission. Cleaned data are merged and linked via token, thus patients are able to be followed longitudinally across plans that contribute data. After Komodo Health finishes processing the data, they are made available as a Snowflake database in the Sentinel cloud environment.

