APPENDIX A. LIST OF INCLUSION, EXCLUSION AND COVARIATE CODES

INCLUSION/EXCLUSION CRITERIA CODES

CODE	ТҮРЕ	DESCRIPTION		
Inclusion c	riteria			
K74.3	ICD10	Primary biliary cholangitis		
571.6	ICD9	Biliary cirrhosis (for rule-out in the baseline period)		
Exclusion of	criteria			
0FY00Z1	ICD10 pcs	Transplantation of liver, syngeneic, open approach		
0FY00Z0	ICD10 pcs	Transplantation of Liver, Allogeneic, Open Approach		
47135	HCPCS/ CPT-4	Liver allotransplantation; orthotopic; partial or whole, from cadaver or living donor, any age		
B17.10	ICD10	Acute hepatitis C without hepatic coma		
B17.11	ICD10	Acute hepatitis C with hepatic coma		
070.41	ICD9	Acute hepatitis C with hepatic coma		
070.51	ICD9	Acute hepatitis C without mention of hepatic coma		
B18.2	ICD10	Chronic viral hepatitis C		
070.44	ICD9	Chronic hepatitis C with hepatic coma		
070.54	ICD9	Chronic hepatitis C without mention of hepatic coma		
070.70	ICD9	Unspecified viral hepatitis C without hepatic coma		
070.71	ICD9	Unspecified viral hepatitis C with hepatic coma		
B16.0	ICD10	Acute hepatitis B with delta-agent with hepatic coma		
B16.1	ICD10	Acute hepatitis B with delta-agent without hepatic coma		
B16.2	ICD10	Acute hepatitis B without delta-agent with hepatic coma		
B16.9	ICD10	Acute hepatitis B without delta-agent and without hepatic coma		
B17.0	ICD10	Acute delta-(super) infection of hepatitis B carrier		
070.20	ICD9	Viral hepatitis B with hepatic coma, acute or unspecified, without mention of hepatitis delta		
070.21	ICD9	Viral hepatitis B with hepatic coma, acute or unspecified, with hepatitis delta		
070.30	ICD9	Viral hepatitis B without mention of hepatic coma, acute or unspecified, without mention of hepatitis delta		
070.31	ICD9	Viral hepatitis B without mention of hepatic coma, acute or unspecified, with hepatitis delta		
B18.0	ICD10	Chronic viral hepatitis B with delta-agent		
B18.1	ICD10	Chronic viral hepatitis B without delta-agent		
070.23	ICD9	Chronic viral hepatitis B with hepatic coma with hepatitis delta		
070.22	ICD9	Chronic viral hepatitis B with hepatic coma without hepatitis delta		
070.33	ICD9	Chronic viral hepatitis B without mention of hepatic coma with hepatitis delta		
070.32	ICD9	Chronic viral hepatitis B without mention of hepatic coma without mention of hepatitis delta		
K83.01	ICD10	Primary sclerosing cholangitis (2019-2021 only)		
K70.0	ICD10	Alcoholic fatty liver		

CODE	ТҮРЕ	DESCRIPTION
K70.10	ICD10	Alcoholic hepatitis without ascites

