070.2	ICD9	Viral hepatitis b with hepatic coma
070.6	ICD9	Unspecified viral hepatitis with hepatic coma
070.4	ICD9	Other specified viral hepatitis with hepatic coma
070.41	ICD9	Acute hepatitis C with hepatic coma
070.6	ICD9	Unspecified viral hepatitis with hepatic coma
070.71	ICD9	Unspecified viral hepatitis C with hepatic coma
Z48.23	ICD10	Encounter for aftercare following liver transplant
V42.7	ICD9	Liver transplant status
T86.40	ICD10	Unspecified complication of liver transplant
T86.41	ICD10	Liver transplant rejection

CODE	ТҮРЕ	DESCRIPTION
T86.42	ICD10	Liver transplant failure
T86.43	ICD10	Liver transplant infection
T86.49	ICD10	Other complications of liver transplant
996.82	ICD9	Complications of transplanted liver

COVARIATE CODES (INLCUDING CHARLESON COMORBIDITY INDEX

CODE	TYPE	DESCRIPTION
K76.6	ICD10	Portal hypertension
572.3	ICD9	Portal hypertension
I86.4	ICD10	Gastric varices
456.8	ICD9	Varices of other sites (non-specific)
I85.00	ICD10	Esophageal varices without bleeding
I85.10	ICD10	Secondary esophageal varices without bleeding
456.1	ICD9	Esophageal varices without mention of bleeding
456.21	ICD9	Esophageal varices in diseases classified elsewhere, without mention of bleeding
K74.5	ICD10	Biliary cirrhosis, unspecified
K74.60	ICD10	Unspecified cirrhosis of liver
K74.69	ICD10	Other cirrhosis of liver
571.5	ICD9	Cirrhosis of liver without mention of alcohol
I21	ICD10	Acute myocardial infarction
I22	ICD10	Subsequent ST elevation and non-ST elevation myocardial infarction
I25.2	ICD10	Old myocardial infarction
410	ICD9	Acute myocardial infarction
412	ICD9	Old myocardial infarction
I11.0	ICD10	Hypertensive heart disease with heart failure
I13.0	ICD10	Hypertensive heart and chronic kidney disease with heart failure and stage 1 through stage 4 chronic kidney disease, or unspecified chronic kidney disease
I13.2	ICD10	Hypertensive heart and chronic kidney disease with heart failure and with stage 5 chronic kidney disease, or end stage renal disease
I25.5	ICD10	Ischemic cardiomyopathy
I42.0	ICD10	Cardiomyopathy
I42.5	ICD10	Other restrictive cardiomyopathy
I42.6	ICD10	Alcoholic cardiomyopathy
I42.7	ICD10	Cardiomyopathy due to drug and external agent
I42.8	ICD10	Other cardiomyopathies
I42.9	ICD10	Cardiomyopathy, unspecified
I43	ICD10	Cardiomyopathy in diseases classified elsewhere
I50	ICD10	Heart failure
P29.0	ICD10	Neonatal cardiac failure
398.91	ICD9	Rheumatic heart failure (congestive)
402.01	ICD9	Malignant hypertensive heart disease with heart failure

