Z94.4	ICD10	Liver transplant status					
070.22	ICD9	Chronic viral hepatitis B with hepatic coma without hepatitis delta					
070.23	ICD9	Chronic viral hepatitis B with hepatic coma with hepatitis delta					
070.32	ICD0	Chronic viral hepatitis B without mention of hepatic coma without mention of					
070.32	ICD9	hepatitis delta					
070.33	ICD9	Chronic viral hepatitis B without mention of hepatic coma with hepatitis delta					
070.44	ICD9	Chronic hepatitis C with hepatic coma					
070.54	ICD9	Chronic hepatitis C without mention of hepatic coma					
070.6	ICD9	inspecified viral hepatitis with hepatic coma					
070.9	ICD9	Unspecified viral hepatitis without mention of hepatic coma					
570	ICD9	Acute and subacute necrosis of liver					
571	ICD9	Chronic liver disease and cirrhosis					
573.3	ICD9	Hepatitis, unspecified					
573.4	ICD9	Hepatic infarction					
573.8	ICD9	Other specified disorders of liver					
573.9	ICD9	Unspecified disorder of liver					
V42.7*	ICD9	Liver replaced by transplant					
E08	ICD10	Diabetes mellitus due to underlying condition					
E09	ICD10	Drug or chemical induced diabetes mellitus					
E10	ICD10	Type 1 diabetes mellitus					
E11	ICD10	Type 2 diabetes mellitus					
E13	ICD10	Other specified diabetes mellitus					
250.8	ICD9	Diabetes with other specified manifestations					
250.9	ICD9	Diabetes with unspecified complication					
249.0	ICD9	Secondary diabetes mellitus without mention of complication					
249.1	ICD9	Secondary diabetes mellitus with ketoacidosis					
249.2	ICD9	Secondary diabetes mellitus with hyperosmolarity					
249.3	ICD9	Secondary diabetes mellitus with other coma					
249.9	ICD9	Secondary diabetes mellitus with unspecified complication, no stated an uncontrolled,					

CODE	TYPE	DESCRIPTION				
		or unspecified				
I12.9	ICD10	Hypertensive chronic kidney disease with stage 1 through stage 4 chronic kidney disease, or unspecified chronic kidney disease				
I13.0	ICD10	Hypertensive heart and chronic kidney disease with heart failure and stage 1 through stage 4 chronic kidney disease, or unspecified chronic kidney disease				
I13.10	ICD10	Hypertensive heart and CKD without heart failure with stage 1 through stage 4 chronic kidney disease, or unspecified chronic kidney disease				
N03	ICD10	Chronic nephritic syndrome				
N05	ICD10	Unspecified nephritic syndrome				
N18.1	ICD10	Chronic kidney disease, Stage 1				
N18.2	ICD10	Chronic kidney disease, Stage 2 (mild)				

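### Komodo study (747-405) only: ICD-10 code Z94.4 is missing from the exclusion table in Appendix A, so the Section 7.3 exclusion of prior liver transplant is not fully implemented

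*Combined protocol and SAP*

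**What the plan says.** Section 7.3 excludes patients with a "History of liver transplant before the index date (inclusive", and sets no limit on how far back the transplant may lie. Section 7.1 states how such criteria are put into operation: "All diagnosis, treatment, laboratory, and procedure codes used to identify patients and define study variables are listed in Appendix A".

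The exclusion table in Appendix A identifies transplant in four ways:

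- procedure codes, beginning with "Transplantation of liver, syngeneic, open approach" (0FY00Z1) and continuing with 0FY00Z0 and CPT 47135;
- the ICD-10 aftercare code Z48.23, "Encounter for aftercare following liver transplant";
- complication codes, namely T86.40 ("Unspecified complication of liver transplant"), T86.41, T86.42, T86.43, T86.49 and ICD-9 996.82;
- the ICD-9 status code V42.7, "Liver transplant status".

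The ICD-10 status code Z94.4 has the same description. It occurs once in the documents, under the heading "COVARIATE CODES (INLCUDING CHARLESON COMORBIDITY INDEX".

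Section 12.1.1 describes the Komodo data as covering patients "between June 2015 and July 2021". Section 7.2 requires a year of enrolment and usable data before index.

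**The concern.** A procedure code shows a transplant only if the operation took place while the patient was in the data. For an earlier transplant, the claims evidence is a status, aftercare or complication code. The exclusion table covers status in ICD-9 but not in ICD-10, and Section 12.4.3 itself treats ICD-10 as the standard coding for US claims. A stable recipient with PBC claims, UDCA use and a raised ALP or bilirubin could therefore satisfy every coded criterion although Section 7.3 means to keep that patient out.

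The coded cohort would then differ from the written one in a study whose composite endpoint includes both transplant and death. Because a patient may supply several control indices, one such recipient could enter the analysis more than once.

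**Working it through.** The plan gives no figure to reproduce. The check is a comparison of code lists.

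**Step 1: count the transplant codes in the exclusion table.** Procedures 3, aftercare 1, ICD-9 status 1, ICD-10 complications 5, ICD-9 complication 1: 3 + 1 + 1 + 5 + 1 = 11. Z94.4 occurs 0 times there and once in the covariate table.

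**Step 2: compare the two status codes.**

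| Code | Exclusion table | Covariate/Charlson table |
|---|---|---|
| V42.7 (ICD-9) | yes | yes |
| Z94.4 (ICD-10) | no | yes |

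The sponsor meant a status code to exclude, and saw no conflict in keeping it in the Charlson list as well. The missing ICD-10 entry therefore looks like an oversight rather than a choice.

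**Step 3: follow a patient through the rules.** Take a Komodo patient transplanted before June 2015, or before their own enrolment began. There is no procedure claim. If later claims carry Z94.4 and none of the eleven listed codes, no exclusion code fires. If the remaining criteria are met, the patient is indexed.

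**Step 4: look for a second line of defence.**

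- Weighting: prior transplant is not among the Section 10.1.1 covariates. Z94.4 can act only through the Charlson score. It is listed close to K74, the family that contains the PBC code K74.3, so a PBC patient may already score that item. The extracted table has no item headings, so this grouping is an inference.
- OPTN: Sections 8.1, 12.1.6 and 12.4.2 use it to establish the transplant endpoint. No section uses it to screen for earlier transplants, and Section 10.1.2 withholds transplant outcomes from study personnel until groups and weights are final.

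**Step 5: can the effect be sized?** Section 10.9 gives the distortion as (OR·P1 + 1 − P1) / (OR·P0 + 1 − P0), where P1 and P0 are the prevalences among OCA-treated and control indices and OR is the association with the outcome. All inputs below are assumptions; none comes from the documents.

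| OR | P1 (OCA) | P0 (control) | Factor |
|---|---|---|---|
| 2 | 0.5% | 1% | 1.005/1.010 = 0.995 |
| 2 | 0 | 1% | 1/1.010 = 0.990 |
| 3 | 0.5% | 2% | 1.010/1.040 = 0.971 |
| 5 | 0 | 2% | 1/1.080 = 0.926 |
| 5 | 0.5% | 0 | 1.020/1 = 1.020 |
| 0.5 | 0 | 2% | 1/0.990 = 1.010 |

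The factor falls on either side of 1, depending on which group holds more recipients and whether their outcomes are worse or better than those of other patients. The table shows only that the direction is open.

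**The case against.** The strongest reply is that claims codes are not the only route to a prior transplant. Komodo is to be linked to OPTN, which Section 12.1.6 describes as covering all US recipients and which supplies transplant dates. A date before index would be visible at the latest when the event data are joined. This has force: it cannot be asserted that such patients would remain in the final analysis. But the plan does not say that a pre-index OPTN date excludes, and the blinding rule keeps this information away while the cohorts are built.

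It is also fair to say that the gap is narrow. Z48.23, the T86.4 codes and, on ICD-9 claims, V42.7 and 996.82 will remove some of these recipients during the year or more of required data. Only those with Z94.4 and nothing else get through.

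Three stronger readings are tempting and are not supported.

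- A reader might infer that both studies are affected. In the Global PBC registry, physicians report transplant and its date on the eCRF (Section 8.1), so the claims code list is not what identifies it.
- A reader might infer a bias in favour of OCA. That requires recipients to be commoner among controls and to fare worse; the documents establish neither. The 0.926 in the table needs every assumed extreme at once.
- A reader might infer that Z94.4 is misplaced in the Charlson list and should be removed. That list follows a cited index and also holds other excluded conditions, V42.7 among them. Its presence there does no harm.

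**Conclusion.** Wrong as written; a minor code-list correction. For the Komodo study, Appendix A does not fully carry out the Section 7.3 transplant exclusion, because V42.7 is in the exclusion table and its ICD-10 counterpart is not. This rests on reading the two tables and on Section 7.1 giving Appendix A its force. The tables were extracted by program, but nothing around the transplant rows suggests a lost line.

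That a recipient could enter follows from the rules. How many would do so is unknown, and so are the size and direction of any effect on the hazard ratio. The case for correction is that the coded rule should match the written one.

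**What to change.** Add one row to the transplant exclusion codes in Appendix A: ICD-10 Z94.4, in any position, on any date up to and including the index date. Do this before the Komodo cohorts are locked. Leave the Charlson list unchanged.

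The cost is one line in the code list and a rerun of the eligibility step. It uses no outcome data and enforces a criterion already in the protocol, so it does not disturb the blinding. Recording in the study log how many patients are removed by this code alone would be optional, and would show how large the gap was.
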